13.3 Data Analysis

At the completion of follow-up in evaluable patients, we will estimate progression-free survival by the Kaplan-Meier method with Greenwood 90% confidence intervals. We will conduct a formal test of the hypothesis that progression-free survival is improved with the experimental therapy. This test will be a one sided exponential test at $\alpha = .10$ that the median progression-free survival is better than 25% compared to historical controls. If this test is significant we will conclude that the progression-free survival is improved compared to the historical control. Descriptive summaries will be prepared of all adverse events by grade, frequency and attribution. An assessment of the association between immune parameters and survival will be conducted. The panel of immune parameters will be tested for association with progression-free and overall survival with Cox proportional hazards regression.

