1. OBJECTIVES

1.1 Primary Objectives

Preliminary data from our laboratory indicate that autologous antigen-loaded α DC1 vaccines induce highly-effective tumor-specific CD8 $^{+}$ CTLs that express defined chemokine receptors, CCR5 and CXCR3.¹⁻³ We have also demonstrated that IFN α and poly-I:C enhance local production of relevant chemokines CCL5/RANTES and CXCL10/IP10 that are able to attract the CCR5- and CXCR3-expressing CTLs selectively to tumor lesions, rather than in marginal healthy tissues. Furthermore, the above factors suppress local production of undesirable chemokines (CCL22) that attract immunosuppressive T_{reg} cells.⁴ In addition, studies have demonstrated a correlation between the density of infiltrating effector T cells and long-term outcomes in malignant peritoneal mesothelioma^{5,6} and colorectal cancer^{7,8}.

In this Phase 1/2 clinical trial, we will test the effectiveness of the treatment of patients with peritoneal surface malignancies, including but not limited to malignant peritoneal mesothelioma (MPM) and peritoneal carcinomatosis (PC) from appendiceal and colorectal primary tumors, using autologous α DC1 vaccines combined with a systemic chemokine modulation regimen, consisting of celecoxib, IFN α , and TLR3 ligand as a component of adjuvant therapy. We anticipate that the resulting tumor-selective modulation of the peritoneal chemokine environment will promote the entry of spontaneously-occurring and α DC1-induced effector-type T (*eff*) cells into tumor, and limit the influx of undesirable regulatory-type T (*reg*) cells.

Our primary objective is to test whether our combined immunotherapy regimen (α DC1 vaccines + CKM) is safe and whether it can prolong time-to-progression (TTP) in patients with peritoneal surface malignancies after optimal CRS + HIPEC with or without adjuvant chemotherapy.

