13. STATISTICAL CONSIDERATIONS

13.1 Study Design/Endpoints

13.1.1 Primary endpoint

- (For Phase 1) Define Recommended Phase 2 Dose (RP2D)

- To evaluate time-to-progression (TTP) in patients with peritoneal surface malignancies (PSM), including but not limited to malignant peritoneal mesothelioma and peritoneal carcinomatosis (PC) of appendiceal and colorectal primary tumors. For patients who will be completely resected, time-to-progression will be equal to recurrence.

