13.2 Power and Sample Size for the Study of Efficacy

Based on information from our prospective database at the University of Pittsburgh over the last 10 years, we expect to treat ~ 115 patients per year (malignant peritoneal mesothelioma ~ 15 cases/year; appendiceal peritoneal carcinomatosis ~ 40 cases/year; colorectal carcinomatosis ~ 60 cases/year). We anticipate approximately 50% of treatment patients will participate in the clinical trial. A review of the literature demonstrates median time-to-progression of 20 months, 20 months and 12 months for malignant peritoneal mesothelioma, appendiceal peritoneal carcinomatosis, and colorectal carcinomatosis, respectively. We aim to demonstrate a 25% improvement in time-to-progression (malignant peritoneal mesothelioma 25 months; appendiceal peritoneal carcinomatosis 25 months; and colorectal carcinomatosis 15 months). We will need 168 patients over 3 years of accrual with an additional 1.5 years of follow-up after accrual ceases. This will provide 90% power to detect an overall improvement of 25% for an exponential test at alpha = 0.10.

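### Section 13.3 words its only formal efficacy test so that, taken literally, the planned 25% improvement becomes the null boundary, in conflict with 1.1, 13.2 and its own neighbouring sentences

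*Combined protocol and SAP*

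**What the plan says.** Section 13.3 (Data Analysis) sets out the efficacy test in three consecutive sentences. The first gives the hypothesis: "We will conduct a formal test of the hypothesis that progression-free survival is improved with the experimental therapy". The second gives the test and its level, "This test will be a one sided exponential test" at alpha 0.10, and the claim being tested: "that the median progression-free survival is better than 25% compared to historical controls". The third gives the conclusion: "If this test is significant we will conclude that the progression-free survival is improved compared to the historical control".

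Section 13.2 takes historical median times to progression of 20, 20 and 12 months (mesothelioma, appendiceal, colorectal) and targets of 25, 25 and 15 months. It plans 168 patients over 3 years of accrual with 1.5 years of further follow-up, and states: "This will provide 90% power to detect an overall improvement of 25% for an exponential test at alpha = 0.10". It also says: "We aim to demonstrate a 25% improvement in time-to-progression".

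Section 1.1 asks whether the regimen "is safe and whether it can prolong time-to-progression (TTP) in patients with peritoneal surface malignancies", with no minimum gain attached. Neither section 13 nor any other part writes the null and alternative hypotheses formally.

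**The concern.** In a one-sided test the claim to be established is the alternative, and its complement is the null. If the claim is a gain of more than 25%, the null is a ratio of at most 1.25. Section 13.2 puts the same 25% on the other side, as the alternative at which power is 90%. The two cannot both describe one test.

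This is the sole formal efficacy rule in a single-arm trial. Observed ratios between roughly 1.12 and 1.41 would pass under one reading and fail under the other, and the planned effect lies inside that interval. If the wording is left open, the choice of rule could be made after the data are known.

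**Working it through.** **Inputs.** From 13.2 and 13.3: one-sided alpha 0.10; power 90%; historical medians 20, 20 and 12 months; ratio 1.25; 168 patients; 36 months accrual; 18 months further follow-up. Assumptions: exponential times, uniform accrual, no dropout, historical medians treated as known. The enrolled tumour mix is not given, so three cases are shown: all patients with a 12-month historical median; a 15:40:60 mix (the centre's yearly caseload in 13.2, assumed to hold for enrolment); all patients with a 20-month historical median.

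**1. The plan's own figure, null ratio 1.0.**

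- Events needed: d = ((1.2816 + 1.2816)/ln 1.25)² = (2.563/0.2231)² = 131.9.
- Probability of an observed event for median m, with L = ln 2/m: 1 − [exp(−18L) − exp(−54L)]/(36L). This is 0.788 for m = 15 and 0.616 for m = 25.
- All patients at 12 versus 15 months: 131.9/0.788 = 167.4, rounded up to 168. With 168 patients there are 132.4 expected events and power is 0.90. This matches the plan.
- The match is exact only in that case. For the 15:40:60 mix, counting events at the target medians gives 118.6 events, power 0.87 and a need for about 187 patients. Counting them at the historical medians gives 130.4 events, power 0.90 and about 170 patients. For all 20-month disease there are 103.5 events, power is 0.84 and about 214 patients are needed (131.9/0.616).

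**2. The same design with null ratio 1.25.** Power at a true ratio r is Φ(√d · ln(r/1.25) − 1.2816). At r = 1.25 the logarithm is zero, so power is Φ(−1.2816) = 0.10 for every d. No sample size gives 90% there, so the power statement in 13.2 cannot belong to this null.

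**3. Observed ratio needed for success.** This is exp(1.2816/√d) under null 1.0, and 1.25 times that under the literal null. The p-value at an observed ratio of 1.25 uses z = √d · ln 1.25 under null 1.0 (2.57, 2.43, 2.27) and z = 0 under the literal null.

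| | All 12-month | 15:40:60 | All 20-month |
|---|---|---|---|
| Expected events at true ratio 1.25 | 132.4 | 118.6 | 103.5 |
| Ratio needed, null 1.0 | 1.12 | 1.12 | 1.13 |
| Ratio needed, literal null 1.25 | 1.40 | 1.41 | 1.42 |
| One-sided p at observed 1.25, null 1.0 | 0.005 | 0.008 | 0.012 |
| One-sided p at observed 1.25, literal | 0.50 | 0.50 | 0.50 |
| Power at true 1.25, null 1.0 | 0.90 | 0.87 | 0.84 |
| Power at true 1.25, literal | 0.10 | 0.10 | 0.10 |
| True ratio for 90% power, literal | 1.58 | 1.61 | 1.64 |

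In months, for 12-month disease: 12 × 1.118 = 13.4 is needed under null 1.0 and 12 × 1.397 = 16.8 under the literal null; the plan is 15. For 20-month disease: 20 × 1.134 = 22.7 and 20 × 1.418 = 28.4; the plan is 25. The planned medians pass the first rule and fail the second.

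**4. False claims of improvement.** For any d the literal threshold is higher, so every literal success is also a success under null 1.0. At a true ratio of 1.0 (143.0, 130.4 and 116.6 events) the literal test succeeds with probability 0.00004, 0.00006 and 0.00011.

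**5. Simulation.** With 40,000 trials of 168 patients under the 15:40:60 mix, each patient's expected events were taken from that patient's own historical median. At a true ratio of 1.25, null 1.0 was rejected in 87.9% of trials and the literal null in 9.4%. At a true ratio of 1.0, the rates were 9.3% and 0.005%.

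**The case against.** The strongest reply is that the documents already settle the matter. The test sentence refers back to a hypothesis of improvement, the next sentence says a significant result means improvement, and 13.2 gives the null medians, the target medians, alpha and power. Only the formal notation is absent. The phrase itself is not a well-formed hypothesis and may be a garbled description of the design alternative. This largely stands, and it is why the sentence is best seen as a slip. It does not remove the need to correct it, because the slip sits in the one sentence that carries the test, its level and its benchmark. The aim in 13.2 to demonstrate a 25% gain also gives the literal reading some footing.

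A second reply is that the 10% is simply alpha at the null boundary, and the p-value of 0.50 is likewise true by construction. That is correct. These figures show what the literal rule would do; they are not separate findings.

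A reader might infer that this trial has only a 10% chance of success, or that the sponsor chose a 25% margin. The documents support neither: both need the literal reading, which 1.1, 13.2 and the adjoining sentences contradict. A reader might also infer a raised false-positive risk; step 4 shows the opposite.

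**Conclusion.** The point holds as an internal contradiction in the primary decision rule. One sentence of 13.3, taken literally, uses as null the effect that 13.2 uses as alternative. The rest of the text favours a null of 1.0, and the wording is probably a slip.

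The harm is conditional on the sentence being applied as written. The rule would then be too strict and would fail a trial that observed exactly its planned medians. That the literal test has 10% power at a ratio of 1.25 needs no assumption on events or mix. The 84% to 90% under null 1.0 and the threshold ranges rest on exponential times, no dropout and the assumed tumour mixes. The exact agreement with 168 patients and 90% power should not be over-read: it requires every patient to have a 12-month historical median. That limit does not rescue a null of 1.25, which cannot give 90% power at 1.25 with any number of patients.

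**What to change.** Replace the test sentence in 13.3 with, for example: *The primary analysis is a one-sided exponential test, alpha 0.10, of H0: ratio of median progression-free survival to historical control ≤ 1.0 against H1: ratio > 1.0; the design alternative is a ratio of 1.25.* This keeps the endpoint name used in the rest of 13.3. Whether the endpoint should be called time to progression, as in 13.1.1 and 13.2, is a separate point, as are the dependence of power on tumour mix and the pooling of the three historical medians. The cost is one sentence; sample size, alpha and data collection do not change.

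If the sponsor does mean to rule out gains of 25% or less, the margin should be stated as the null and the power statement in 13.2 rewritten: 10% at a ratio of 1.25, and 90% only at about 1.58 to 1.64. That option is not cost-free, because the present design would then lack power for its planned effect.

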2.6 Chemokine Modulatory Regimen

2.6.1 Critical role of chemokine-driven T cell migration in cancers

The numbers of effector T cells in malignant peritoneal mesothelioma and CRC tissues have been shown to be an independent prognostic marker, with high numbers predicting a delayed

time to cancer recurrence.⁵⁻⁸ In contrast, regulatory T cells in CRC patients are associated with poor tumor response.⁴⁴⁻⁴⁶ Chemokines and their respective receptors are critical for T cell migration and homing into tissues during homeostasis and inflammation.^{47,48} Several studies have shown that CXCR3 and CCR5 are critical for T cell entry into tumors, which is guided by intra-tumoral expression of respective chemokines. High levels of the chemokine ligands for CCR5 (CCL5/RANTES and CXCR3/IP10) in tumor tissue have been associated with infiltration of CD8 T cells with respective receptors in CRC,⁴⁹ as well as melanoma⁵⁰ and gastric cancer.⁵¹ High CXCR3⁺ T cells in peripheral circulation has been associated with increased survival of stage III melanoma patients.⁵² In contrast, high levels of CCL22 (ligand for CCR4) expression by DC or macrophages in ovarian ascites recruit regulatory T cells and is associated with decreased patient survival⁴³. But most tumors do not have T cell infiltration, or express the correct chemokines for effector T cell (T_{eff}) entry. Colon tumors frequently show elevated CCL22 levels induced by a PGE₂ rich tumor microenvironment^{53,54} permitting regulatory T cells (T_{reg}) rather than T_{eff} cells, leading to highly biased T_{reg}/T_{eff} ratio in tumors. The current study attempts to correct the above mentioned chemokine bias in the tumor microenvironment using a chemokine modulation regimen and analyze whether such modulation can help T_{eff} entry and prevent T_{reg}s influx into tumors.

2.6.2 Past experience with chemokine modulation agents TLR3 ligands, IFN α , and celecoxib

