9. CORRELATIVE STUDIES

At indicated time points (see the study calendar, Section 10) up to 60 cc of peripheral blood will be collected and cryopreserved for potential correlative studies. For additional correlative studies, we may cryopreserve the available portions of the harvested tumors, not used for the preparation of autologous vaccines. The exact scope of the correlative studies will depend on the clinical outcomes and available funding, but may include:

- Changes in circulating subsets of immune cells (flow cytometry).
- Changes in serum immune mediators, cytokines, chemokines (Luminex, ELISAs).
- Changes in gene expression of blood cells (mRNA/Taqman assays).
- Changes in the frequencies and activity of tumor-reactive cells (ELISPOTs and ELISAs)

TTP may be correlated with the changes in the blood samples from the treated subjects. For subjects who will need palliative surgery or will demonstrate clinical response and will have accessible tumor tissue, we may obtain tumor material to analyze tumor-infiltrating CD8⁺ T cells in the resected metastatic CRC lesions and local expression of chemokines and other inflammatory mediators. This is measured as the ratio between the CD8 (or other gene) mRNA message and the expression of the housekeeping gene HPRT, in situ hybridization [ISH], and Immunohistochemistry/immunofluorescence [ICH/IF]. Examples of additional relevant parameters include total numbers of infiltrating T cells, their CD4/CD8 ratios, frequencies of FoxP3 cells, and the expression of chemokine receptors on CD4⁺ and CD8⁺ T cells (CXCR3, CCR5, CCR4, CCR6, and CXCR4). Using ISH, IF, and Taqman, we may also evaluate the local expression of T_{eff}-attracting chemokines: CCR5, CXCL9, and CXCL10 and CXCL11, and MDSC/T_{reg}-attracting chemokines: CCL22 and CXCL12. Similar assays may also be performed on any available pre-treatment tumors (if such material will remain after preparation of vaccines).

These potential correlative studies may allow us to determine if any blood- or tumor-associated markers are predictive of response to treatment and thus may be used as prospective inclusion criteria or assist us in prospective decisions regarding continuation of treatment in the individual patients. They may also facilitate development of additional therapies.

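### The immune-marker Cox models name no stratum or covariate for tumour type, so a blood marker that differs between colorectal and other patients has a raised false-positive rate for progression; and one arm cannot show a marker to be predictive

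*Combined protocol and SAP*

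**What the plan says.** Section 13.3 states: "The panel of immune parameters will be tested for association with progression-free and overall survival with Cox proportional hazards regression". It gives no strata, covariates or significance level for these tests, and no other section adjusts any analysis for tumour type.

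Section 13.2 gives outcome by tumour type: "median time-to-progression of 20 months, 20 months and 12 months for malignant peritoneal mesothelioma, appendiceal peritoneal carcinomatosis, and colorectal carcinomatosis, respectively". The targets are "malignant peritoneal mesothelioma 25 months; appendiceal peritoneal carcinomatosis 25 months; and colorectal carcinomatosis 15 months". The expected yearly caseload is "malignant peritoneal mesothelioma ~ 15 cases/year; appendiceal peritoneal carcinomatosis ~ 40 cases/year; colorectal carcinomatosis ~ 60 cases/year".

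On use of the results, section 1.2 seeks predictive markers of clinical benefit. Section 9 says the correlative studies may show whether blood or tumour markers are "predictive of response to treatment and thus may be used as prospective inclusion criteria", or may help decide whether individual patients continue treatment. The efficacy comparison in section 13.3 is with historical controls. There is one treated group.

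**The concern.** Tumour type is a strong outcome factor on the plan's own figures, is known for every patient, and is absent from the specified model. If a marker's level also differs by tumour type, an unadjusted Cox model credits the marker with the hazard difference that belongs to the type.

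A second issue is separate and does not depend on the first. Where everyone receives the treatment, an association between a marker and outcome may mean that the marker identifies patients who benefit, or only patients who would do well anyway. The protocol shows why this matters: section 2.6.1 says effector T-cell numbers in tumour tissue "have been shown to be an independent prognostic marker", on evidence from patients who did not receive this regimen.

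At stake is the reading of a named secondary objective. The primary test, the sample size and the safety rule are untouched.

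**Working it through.** **Inputs from section 13.2.** Medians 20/20/12 months (targets 25/25/15); caseload 15:40:60 per 115; 168 patients; 36 months of accrual; 18 months of further follow-up.

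**Assumptions.** Exponential times; participants follow the caseload mix; TTP and PFS treated alike; marker tests two-sided at 5% (the plan gives no level); marker prevalence by type, shown as a range.

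**1. The plan's own figure.** Events for the one-sided exponential test at 0.10 with 90% power: ((1.2816 + 1.2816)/ln 1.25)² = 131.9. With hazard λ = ln 2/median, the event probability is 1 − (e^(−18λ) − e^(−54λ))/(36λ): 0.694 at 20 months and 0.851 at 12 months. Over the mix this is (55 × 0.694 + 60 × 0.851)/115 = 0.776. Then N = 131.9/0.776 = 170, close to the stated 168. So these settings are near those behind the plan. Expected events in 168 patients: 168 × 0.776 = 130 (119 at the target medians).

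**2. Hazard ratio between types.** Colorectal against the other two: 20/12 = 1.67. At the targets, 25/15 = 1.67.

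**3. How a null marker picks this up.** Take a marker with no effect within any type. Per 115 patients at prevalence 70/70/30, marker-positives number 55 × 0.7 = 38.5 non-colorectal and 60 × 0.3 = 18 colorectal, so 18/56.5 = 32% are colorectal. Among marker-negatives it is 42/58.5 = 72%. If only mesothelioma differs (70/30/30), the shares are 18/40.5 = 44% and 42/74.5 = 56%, so little hazard difference is carried over.

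**4. Simulated rejection rates.** 168 patients, no marker effect within type, medians 20/20/12, 6,000 trials per row, Cox score test:

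| Prevalence, meso/appendiceal/colorectal | Colorectal share, marker + / − | No stratum | Stratified by type |
|---|---|---|---|
| 50/50/50 | 52% / 52% | 4.9% | 5.2% |
| 60/60/40 | 42% / 62% | 8.8% | 5.3% |
| 70/50/30 | 37% / 63% | 11.0% | 5.1% |
| 70/70/30 | 32% / 72% | 21.7% | 5.2% |
| 60/40/40 | 49% / 55% | 5.1% | 4.9% |
| 70/30/30 | 44% / 56% | 6.1% | 5.4% |

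Repeat runs gave 7.8 to 10.6% at 60/60/40 and 19 to 22% at 70/70/30. The apparent hazard ratios were about 0.90 and 0.82 where the truth is 1. At the target medians the unstratified rates were 8.5%, 10.2% and 18.1% for rows two to four.

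**5. Continuous marker.** A colorectal shift of 0.25, 0.5, 1.0 or 1.5 SD gave 6.8, 10.6, 24.0 and 40.7% without a stratum, against 4.8 to 5.6% stratified. A marker identical to colorectal origin gave 82%. A 1 SD shift in mesothelioma alone gave about 7%.

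**6. Checks.** With all medians set to 16 months, the unstratified test stayed at 4.5 to 5.8%, so the difference in medians is the cause. With only 60 patients analysed and the target medians, a 1 SD colorectal shift gave 11.8% unstratified and 5.4% stratified, so the inflation shrinks with fewer patients.

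**The case against.** The strongest objection is that the inflation needs colorectal patients to differ from both other groups. Section 2.3 expects appendiceal immunogenicity to resemble colorectal. On that expectation a marker would separate mesothelioma (15/115 = 13%) from the rest, while the hazard separates colorectal from the rest; the two barely align and the rate stays near nominal. This stands. It limits the size of the concern, but it is an expectation stated where the protocol says research is lacking, not data on blood markers.

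It is also fair that the immune differences in the background come mostly from tumour tissue, and the mesothelioma patient data are pleural, whereas the planned panel is mainly peripheral blood and largely within-patient change. No section gives blood-marker levels by tumour type.

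Three stronger readings are tempting, and the documents do not support them:

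- A reader might infer that any marker tracking tumour type will test as associated. Outside near-perfect proxies the result is a raised probability, and most such markers would still not reach significance.
- A reader might infer that the plan commits to an unadjusted pooled model. Section 13.3 is silent: it neither names covariates nor rules them out.
- A reader might infer that the marker work is the main secondary output and will select patients. Overall survival is listed first, section 9 makes the scope depend on outcomes and funding, and its wording on use is hedged throughout. Section 13.3 itself claims only association.

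Hedging does not answer the second issue: the design cannot distinguish predictive from prognostic however cautiously the aim is phrased.

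**Conclusion.** The point holds in a conditional form. As specified, the marker models leave out a factor that the plan expects to change the hazard of progression by 1.67. For a marker that differs between colorectal and the other types, the nominal 5% error rate for TTP/PFS rises to about 8-11% for a modest difference (60/60/40), about 11% for a graded one (70/50/30) and about 20% for a large one (70/70/30). If prevalence is equal, or only mesothelioma differs, it stays near 5-6% (about 7% for a 1 SD mesothelioma shift).

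These sizes rest on assumed prevalences, the clinic mix, exponential times and an assumed 5% level. Eligibility also admits other primaries, for which no median is given. For overall survival, sections 2.1 and 2.2 give only overlapping ranges after cytoreduction with intraperitoneal chemotherapy (36 to 92 months for mesothelioma, 30 to 60 for colorectal) and section 2.3 gives no appendiceal median, so that effect is not quantified.

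The second conclusion needs no such assumptions: without a concurrent control, this analysis can show association with outcome but not prediction of treatment benefit. Stratifying does not change that.

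**What to change.** In section 13.3, state that the immune-parameter Cox models are stratified by primary tumour type (mesothelioma, appendiceal, colorectal, other). This takes one sentence and no new data, visits or patients. The cost is a slight loss of precision; small strata, such as mesothelioma or other primaries, will add little information.

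In sections 1.2 and 9, describe such markers as associated with outcome and hypothesis-generating, rather than predictive of response or clinical benefit. The cost is a more modest biomarker claim.

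Any decision on inclusion criteria or continuation of treatment remains with the sponsor. The protocol need only note that this single-arm analysis cannot by itself support one.

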6. Peripheral blood for potential correlative studies will be collected at the following time points: once during the pre-screening, within 60 minutes before the vaccinations of the priming cycle, and booster cycles 1 and 2; and within 60 minutes after completing booster cycle 2 on Friday. Peripheral blood for potential correlative studies may additionally be drawn within 60 minutes before the vaccination of booster cycle 3 on Monday and within 60 minutes after completing booster cycles 1 and 3 on Friday.
7. Performed within 2 weeks prior to the priming dose of vaccine and 5 business days prior to cycles 1, 2 and 3 vaccines.
8. CT or MRI imaging should be performed prior to cycle 1 if the recovery period from surgery is greater than 6 weeks.
9. At the discretion of the treating physician, the tests/procedures due to be performed at the Off Study Treatment visit may be performed on the last day of the CKM treatment for scheduling purposes.
10. Performed as routine pre-operative evaluation.
11. AEs /conmeds should be collected up to 5 days after treatment, unless considered clinically significant or serious in nature in which case they will be followed until resolution or Grade 1.

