11.3 Duration of Response

Time-to-Progression (TTP): Time-to-Progression is measured from the start of treatment until the criteria for progression are met

Duration of overall response: The duration of overall response is measured from the time of surgical resection until the first date that progressive disease is objectively documented (taking as reference for progressive disease the smallest measurements recorded since the treatment started).

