13.1.2 Secondary endpoints

- To estimate overall survival (OS).
- Correlative studies to characterize sequential immune response changes by quantitative measures of immune cellular phenotypes and chemokine patterns in peripheral blood (see Section 9). These results will be correlated with TTP, PFS, and OS.

Note the additional discussion of the Phase 1 dose-finding studies described in Section 5.1.

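### Section 13.3 sets no landmark or time-dependent handling for on-treatment immune markers, so some ordinary marker summaries can make an inert marker look protective

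*Combined protocol and SAP*

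**What the plan says.** Section 13.3 gives the marker analysis one operative sentence: "The panel of immune parameters will be tested for association with progression-free and overall survival with Cox proportional hazards regression". It does not say which sample or summary enters the model, or what happens to patients without later samples.

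The markers are mainly post-baseline. Section 13.1.2 lists as a secondary endpoint "Correlative studies to characterize sequential immune response changes by quantitative measures of immune cellular phenotypes and chemokine patterns in peripheral blood", and adds: "These results will be correlated with TTP, PFS, and OS". Section 9 says: "TTP may be correlated with the changes in the blood samples from the treated subjects".

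Section 10, footnote 6, sets required samples "once during the pre-screening, within 60 minutes before the vaccinations of the priming cycle, and booster cycles 1 and 2", plus one after booster 2. Optional samples may be taken "within 60 minutes before the vaccination of booster cycle 3 on Monday and within 60 minutes after completing booster cycles 1 and 3 on Friday".

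On the clock, Section 11.3 states: "Time-to-Progression is measured from the start of treatment until the criteria for progression are met". No separate origin is given for PFS or OS. Section 5.7 ends treatment at progression, except for progression between surgery and the CKM regimen. Section 5.2 allows 4 to 12 weeks between cycles, with a target of 4.

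**The concern.** The number of on-treatment samples a patient contributes depends on how long that patient stays progression-free. An early progressor has one or two samples; a patient who completes treatment has several. If the marker is summarised over whatever samples exist and related to time from treatment start, part of the marker is a record of event-free time already survived. This is guarantee-time (immortal-time) bias, and it favours the marker.

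The association with TTP, PFS and OS is a listed secondary endpoint. Section 9 also foresees that markers found this way may later serve to select patients or inform whether an individual continues treatment. A marker that mostly counts cycles received would be a poor basis for either.

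**Working it through.** **The plan's own figure.** The documents give no figure for the marker analysis, so the planning model of Section 13.2 is reproduced first, because the check uses it. Events = (1.2816 + 1.2816)² / (ln 1.25)² = 131.9. With 36 months' uniform accrual (A) and 18 months' further follow-up (F), the event probability is 1 − [exp(−λF) − exp(−λ(A+F))]/(λA). At historical medians of 20, 20 and 12 months and a case mix of 15:40:60, this is 0.776. Then N = 131.9/0.776 = 170, and power at 168 is 0.897. The stated 168 patients and 90% power are reproduced closely.

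**When the samples fall.** With gaps of 4 to 12 weeks, booster 2 falls 8 to 24 weeks after priming and booster 3 falls 12 to 36 weeks after it.

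**Who has progressed by then.** P(progressed by t) = 1 − 2^(−t/median), averaged over the case mix:

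| Week | Historical medians | Improved medians (25/25/15) |
|---|---|---|
| 8 | 8% | 7% |
| 12 | 12% | 10% |
| 24 | 23% | 18% |
| 36 | 32% | 26% |

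**Simulation set-up.** 168 patients; improved medians, case mix, accrual and follow-up from Section 13.2; exponential times; the marker has no effect on outcome (true HR 1). Gaps are exactly 4 weeks (target) or uniform on 4 to 12 weeks (full windows).

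**Marker that rises with each cycle, last available value, Cox from treatment start.** The assumed rise per cycle is not in the documents. Share of trials with p<0.05:

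| Timing and samples | 0.3 SD | 0.5 SD | 1.0 SD |
|---|---|---|---|
| Target, required samples | 6% | 10% | 35% |
| Target, with booster 3 | 16% | 31% | 78% |
| Full windows, required samples | 14% | 34% | 76% |
| Full windows, with booster 3 | 39% | 72% | 100% |

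The spurious HR per unit is about 0.95/0.93/0.88 in the first row and 0.86/0.78/0.63 in the last. With no rise, the last available value rejects in 3 to 5%.

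**Pure-noise marker with no trend, other summaries** (target / full windows; the first two use booster 3 samples):
- responder at any sample (25% cut-off per sample assumed): HR 0.71 / 0.55, rejection 42% / 84%;
- maximum change over available samples: HR 0.84 / 0.73, rejection 22% / 58%;
- responder after booster 2 (50% cut-off assumed), unsampled patients counted as non-responders: HR 0.84 / 0.69, rejection 16% / 48%.

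**Analyses that behave properly.** The post-booster-2 value in sampled patients only gives HR 1.01 / 0.99 and rejection 6% / 4%. No analysed patient can have an event before the sample, so this is nearly a landmark analysis. A landmark after the last sample returns the any-sample responder coding to HR about 1.00 and rejection of about 4 to 8%.

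Monte Carlo error is about 1 to 2.5 percentage points.

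**Events lost to a landmark.** Total event probability at the improved medians is 0.706.
- Booster 2 at week 8: 0.066/0.706 = 9%.
- Booster 2 at week 16, the centre of the full windows (3.68 months): (55 × 0.097 + 60 × 0.156)/115 = 0.128, and 0.128/0.706 = 18%.
- Week 36: 0.264/0.706 = 37% (about 35% in simulation).

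**The case against.** A reader might infer that the plan enters on-treatment values as if known at treatment start, and that false associations follow. The documents do not support that. Section 13.3 is silent on how the values enter, a time-dependent model is also Cox regression, and the treatment-start origin is explicit only for TTP. Bias needs a further choice: a summary that grows with the number of samples, or unsampled patients coded as non-responders. Pre-screening and pre-priming values cannot be affected.

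A reader might also take the 39/72/100% row as the expected size. It combines an assumed rise, gaps spread over the whole window although every target is 4 weeks, and booster 3 samples that are optional. Detection matters too: the one scan scheduled during treatment precedes booster 2 (Section 11). If progression is found only at scheduled scans, target timing gives 8/6/15% with required samples and 7/12/39% with booster 3.

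Finally, Section 9 calls these studies potential and dependent on funding, and any use for selection or continuation is prospective. No decision in this trial rests on them.

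All of this stands as a limit on size and wording. It does not supply the missing rule. The regimen is designed to build an immune response over repeated boosters (Sections 2.7.2 and 5.2), so a marker that rises by cycle is plausible. Any-sample response and maximum change are ordinary summaries that 13.3 leaves open.

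**Conclusion.** The point holds as a conditional weakness in a secondary analysis. The markers are largely on-treatment changes, the number of samples depends on the outcome, and Section 13.3 has no safeguard. Depending on the unspecified summary and on cycle timing, the false-positive rate for an inert marker runs from about 5% to over 80% without any trend. For the last available value of a rising marker it runs from 6% to 100%.

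These sizes rest on assumptions outside the documents: the rise per cycle, the responder cut-offs, exponential times, independent sample noise, the distribution of gaps, and sampling that stops at progression. All figures concern progression; the effect on OS was not quantified. A reader should not extend the point to the primary test, to pre-treatment markers, or to a single fixed-visit value in sampled patients. For that last analysis the cost is that the result does not describe early progressors.

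**What to change.** Amend Section 13.3 to:
- name the marker time point or summary, and state how patients without the sample are handled (not as non-responders);
- enter pre-treatment markers as fixed covariates;
- analyse on-treatment markers either as time-dependent covariates, or from a landmark at a named sampling visit (for example booster 2) among patients progression-free and sampled at that visit, with the clock restarted there;
- state the time origin for PFS and OS.

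No new visits, samples or patients are needed. The cost is events: a booster 2 landmark loses about 9 to 18% of progression events, and a 36-week landmark about 35 to 37%. The early landmark or the time-dependent model is therefore preferable. A landmark result applies only to patients still progression-free at that visit, and should be reported that way.
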